## ABBREVIATIONS

AE	Adverse Event
ALT	Alanine Transaminase
AMG	Arzneimittelgesetz
AML	Acute Myeloid Leukemia
AMLCG	AML Cooperative Group
ANC	Absolute Neutrophil Count
AP	Alkaline Phosphatase
APL	Acute Promyelocytic Leukemia
AR	Adverse Reaction
AraC	Cytosine Arabinoside
AST	Aspartate Transaminase
AT III	Antithrombin III
ATP	Adenosin Triphosphate
AUC	Area Under the Curve
BID	twice daily
BM	Bone Marrow
BP	Blood Pressure
BSA	Body Surface Area
CBC	Complete Blood Count
CFR	Code of Federal regulations
CNS	Central Nervous System
CR	Complete Remission
CRi	Complete Remission with incomplete regeneration of peripheral blood
CRc	Complete Cytogenetic Remission
CRm	Complete Moleculargenetic Remission
CRA	Clinical Research Associate
CrCl	Creatinin Clearance
CRF	Case Report Form
CT	Chemotherapy
CTCAE	Common Toxicity Criteria for Adverse Events
CYP	Cytochrome P
DLT	Dose Limiting Toxicities
DNA	Desoxyribonucleic Acid
DSIL	Deutsche Studieninitiative Leukämie
DSMB	Data Safety Monitoring Board
ECG	Electrocardiogram
ED	Early Death
ECOG	Eastern Cooperative Oncology Group
EDTA	Ethylenediaminetetraacetic acid

EFS	Event Free Survival
FAB	French-American-British Cooperative Group
FDA	Food and Drug Administration
Flt	Fms like Tyrosine Kinase
FISH	Fluorescence In Situ Hybridization
GCP	Good Clinical Practice
G-CSF	Granulocyte Colony Stimulating Factor
GI	Gastrointestinal
GM-CSF	Granulocyte Macrophage Colony Stimulating Factor
HCC	HepatoCellular Cancer
HD-AraC	High Dose-Cytarabine
HFSR	Hand-Foot Skin Reaction
HIV	Human Immunodeficiency Virus
HR	cytogenetically High Risk
ICH	International Conference on Harmonization
INR	International Normalized Ratio
IR	cytogenetically Intermediate Risk
IRB/IEC	Institutional Review Board/ Independent Ethics Committee
ITD	Internal Tandem Duplication
ITT	Intention To Treat analysis
LDH	Lactatedehydrogenase
LKP	Leiter der Klinischen Prüfung
LR	cytogenetically Low Risk
MAPK	mitogen-activated protein kinase
MDS	Myelodysplastic Syndrome
mg	miligram
MI	Myocardial Infarction
mm	millimeter
MRD	Minimal Residual Disease
NCI-CTC	National Cancer Institute Common Toxicity Criteria
nM	nanoMol
NPM	Nucleophosmin
OS	Overall Survival
PB	Peripheral Blood
PDGF	Platelet-Derived Growth Factor
PDGFR	Platelet-Derived Growth Factor Receptor
PE	Physical Examination
PK	Pharmacokinetic
p.o.	per os = per mouth
PR	Partial Response
PT-INR	Prothrombin Time-International Normalized Ratio

PTT	Partial Thromboplastin Time
QOD	Once Every Other Day
QD	Once Every Day
RNA	Ribonucleic Acid
SAE	Serious Adverse Event
SAL	Study Alliance Leukemia
SAR	Serious Adverse Reaction
SCF	Stem Cell Factor
SOP	Standard Operating Procedure
sqm	square meters
SUSAR	Suspected Unexpected Adverse Reaction
Tx	Stem Cell Transplantation
UAR	Unexpected Adverse Reaction
ULN	Upper Limit of Normal
VEGF	Vascular Endothelial Growth Factor
VEGFR	Vascular Endothelial Growth Factor Receptor
WHO	World Health Organization
WT	Wild Type

# **1 BACKGROUND INFORMATION / INTRODUCTION**

## **1.1 Condition background and current treatment**

Acute Myeloid Leukemia (AML) is a clonal, malignant disorder that results from a somatic mutation in a pluripotent stem cell or a slightly more differentiated progenitor cell. The mutant cell gains a growth and/or survival advantage in relationship to the normal pool of stem cells. Fewer than 30% of adults with AML can be expected to survive three or more years and be cured. Adverse prognostic factors include poor ECOG performance status prior to therapy, secondary AML, a white cell count of more than 20.000/ $\mu$ l or an elevated serum lactate dehydrogenase at presentation. Detailed cytogenetic analysis of the leukemic blasts has also been demonstrated to provide critical prognostic information. Initial AML treatment is divided into two phases: induction and consolidation. With the use of cytarabine and an anthracycline as induction therapy, complete remissions can be routinely induced in 70%-80% of patients 60 years and younger and in approximately 50% of older patients. Consolidation therapy following the induction of an initial complete response is essential to prevent relapse. Three options are available: allogeneic or autologous bone marrow transplantation or chemotherapy. Transplantation is more often used in young patients with adverse karyotypes and chemotherapy in good prognosis patients. Nontransplant consolidation chemotherapy regimens commonly contain cytarabine. There appears to be a clear benefit in survival to patients younger than 60 years of age that received high-dose cytarabine regimens as consolidation.

Generally accepted risk criteria for the assessment of prognosis are cytogenetic criteria which define either low risk or high risk (for a compilation see chapter.3.3.2). Moreover, only recently it was described that an insufficient response to induction chemotherapy is highly predictable for therapy outcome. A critical threshold for residual blast cells at the day 16 bone marrow control has been defined with  $\leq 10\%$  of marrow cellularity.

## **1.2 Molecular pathogenesis**

In the last decades, significant progress has been made about the molecular events inducing leukemic transformation in AML (for review). Although AML is a genetically and phenotypically heterogeneous disease, common features of the leukemic blasts include a high proliferative potential and a block in differentiation at a relatively immature state, within the mitotic pool. It is now widely accepted that AML blasts already harbor several transforming mutations when the disease becomes clinically apparent. Many AML-specific oncogenic mutations have been identified and their ability to cause leukemia has been analyzed in primary and human xenograft mouse models. A model has been suggested that at least two mutations from different

complementation classes have to accumulate in a myeloid progenitor cell to cause AML. One of these mutations is thought to cause deregulation of transcriptional programs needed for the orchestration of myeloid differentiation. Thus, more than 50% of all AML cases have been shown to contain a mutation in a transcriptional regulator, often as a result from balanced reciprocal translocations.

These mutations often coincide with mutations in signal transduction mediators. Again, about 50% of AML cases have been shown to contain a mutation in a signaling mediator, most frequently in receptor tyrosine kinases or in the Ras oncogene. The receptor tyrosine kinase Flt3 has been found to be the most common target among these, in 30% of all AML cases (for review). Flt3 mutations have been shown in several *in vitro* and animal models to cause malignant transformation of myeloid cells and to cooperate with other known oncogenes to cause an AML-type disease in mice.

The more common type of Flt3-mutations, so-called internal tandem duplications (ITD), are associated with a bad prognosis of AML patients, especially when the normal Flt3 allele is lost in the majority of blasts. Flt3 mutations are very frequently associated with mutations in the gene for nucleophosmin (NPM), a protein with functions in organizing the traffic of proteins between the nucleus and the cytoplasm. The functional consequences of these mutations are not yet known. However, the presence of these mutations in AML blasts is a strong positive prognostic indicator. Several phase-I and phase-II trials have been reported where AML patients in later stages of the disease were treated with tyrosine kinase inhibitors that target Flt3 as single agents. In these trials, biological activity of the compounds was noted, albeit with very low complete remission rates (for review). Thus, Flt3 is thought to be a promising target for the treatment of AML.

Other very common mutations in a signal transduction mediator are oncogenic N- and K-Ras mutations that have been described in AML for over 20 years, with a prevalence of slightly less than 30%. One important effector of oncogenic Ras is, among others, the Raf/MAP-kinase pathway that relays important cellular functions like proliferation, survival and differentiation (see below).

In summary, AML is thought to be the result of multiple genetic events including activating mutations in signal transduction mediators.

### **1.3 Investigational product background**

Sorafenib is a novel RAF, Flt3, VEGFR and c-Kit kinase inhibitor that prevents tumor growth by combining two anticancer activities: inhibition of tumor cell proliferation and tumor angiogenesis. For full details of the pre-clinical and clinical information please refer to the Nexavar® Prescribing Information (Fachinformation).

### 1.3.1 Pre-clinical information

#### **General information**

Bayer and Onyx developed Sorafenib (BAY-43-9006), an oral cytostatic Raf kinase inhibitor, PDGFR inhibitor and VEGFR-2 (KDR) inhibitor, for the potential treatment of various cancers.

Sorafenib was selected based on the inhibition of the enzyme, Raf kinase, in a battery of biochemical, cellular, and *in vivo* assays and its broad-spectrum antitumor efficacy in pre-clinical xenograft models. In other cellular assays, Sorafenib was found to be a potent inhibitor of human and mouse VEGFR-2, VEGFR-3, PDGFR- $\alpha$ , c-Kit and Flt3 receptor phosphorylation.

Sorafenib functions by inhibiting the Raf kinase constituent of the classical mitogen-activated protein kinase (MAPK) signaling cascade. Raf and other members (such as Ras) of this pathway are attractive targets for development of antineoplastic agents because their aberrant activity has been heavily implicated in the onset of a variety of cancers. Protein kinases possess enzymatic activity that enables intracellular signaling via a series of phosphorylation events. This intricate process is initiated upon ligand-receptor interaction at the cellular membrane. Kinase activation is then mediated through the removal of the gamma-phosphate group of ATP and subsequent transferral to a tyrosine, serine or threonine residue on its downstream substrate. Events such as these ultimately control mitogenic signals that facilitate alterations in nuclear gene expression. When properly regulated, the classical MAPK (Raf/MEK/ERK) pathway controls a variety of cellular functions such as proliferation, differentiation, and apoptosis. Genetic mutations can, however, lead to overexpression or aberrant activity of a particular MAPK. Furthermore, it is widely known that MAPK hyperactivity can lead to tumorigenesis.

More recently, it has also been shown that Sorafenib is a strong inhibitor of the receptor tyrosine kinase Flt3 that has been implicated in the pathogenesis of AML. Also, Sorafenib inhibits the activity of VEGF receptors that have been shown to be expressed on the surface of AML blasts as well as on the surface of surrounding bone marrow microvessels. Microvessel density is greatly increased in AML bone marrow and it is possible that by inhibition of VEGF receptors, leukemia-induced neoangiogenesis is targeted, providing a further rationale for the treatment of AML with Sorafenib. Moreover, only recently it was shown that Sorafenib has a potent inhibitory activity against Kit activating mutations. Although, the activity of Sorafenib against the D816 mutation is lower most of the activating mutations will be inhibited in the low nM range. Additionally it has been found that Sorafenib is able to modify the balance of pro/antiapoptotic proteins even in cells without mutations of the Flt3 or Kit kinase. Most of the effects are assumed to depend on the downregulation of the antiapoptotic proteins Mcl1 and FLIPL.

In summary, Sorafenib targets molecular pathways that have been implicated in the pathogenesis of AML. The highest efficacy of Sorafenib is related to the inhibition of tyrosine

kinase pathways including the classical MAPK pathway, angiogenic VEGF receptors and the receptor tyrosine kinases Flt3 and c-Kit.

### ***Combination with chemotherapeutic agents***

Sorafenib can be safely combined with a variety of standard cancer chemotherapy agents, including paclitaxel, irinotecan, gemcitabine and cisplatin with no significant increase in the toxicity associated with those agents and without diminishing their antitumor efficacy in clinical investigations.

### ***Pre-clinical pharmacokinetics***

- Absorption in mice and rats was almost complete and in dogs approx. 68 %
- High bioavailability in mice and rats (approx. 80 %) and moderate in dogs (approx. 60 %)
- Slow to moderate elimination of Sorafenib from plasma with terminal half-lives of 9 h (rats), 6 h (mice), 4 h (dogs)
- Rapid and homogeneous distribution to almost all organs/tissues in rats, low penetration of blood/brain barrier
- Low residues, no evidence of irreversible binding or retention in organs or tissues of rats
- Sorafenib showed a potency to inhibit CYP isoforms *in vitro* and clinically relevant drug-drug interactions cannot be ruled out
- Excretion of the compound is primarily via the biliary/ fecal route in rats and dogs.

### ***Pre-clinical toxicology***

The pre-clinical toxicity profile of Sorafenib can be summarized as:

- Short-term high-dose treatment was well tolerated clinically by rats, mice and dogs; a plateau in systemic exposure was observed.
- Exposure-dependent mortality (mean time to death  $\geq 3$  weeks) occurred without preceding specific signs of morbidity in rats; dose-limiting toxicity in dogs was gastrointestinal (emesis, bloody diarrhea). Clinical signs of toxicity were unspecific, except for marked skin reactions in dogs. A lower threshold-dose for significant toxicities was observed with extensive duration of exposure.
- Histopathology revealed degeneration/regeneration processes in multiple organ systems including liver, kidneys, lymphoreticular/hematopoietic system, GI tract, pancreas, adrenals, reproductive organs, skin, teeth, and bone. No main target organ of toxicity could be identified; some morphological lesions were not reversible within 4 weeks (e.g., bile duct proliferation, liver fibrosis, adrenal necrosis, effects on lymphoreticular system) following a 4-week course of treatment.

- Based on genotoxicity assays conducted, Sorafenib is concluded not to exhibit a significant risk of genotoxicity to patients.
- Sorafenib was nontoxic following a single oral administration to dogs, rats or mice. Potential acutely lethal levels might not be achievable due to limited systemic exposure.

In conclusion, toxicity studies with Sorafenib in rats, mice and dogs, species considered appropriate for the pre-clinical safety evaluation, demonstrated multiple target organs, dose-limiting toxicities and clear dose and time effect relations. For further information about pre-clinical data of Sorafenib, please refer to the Nexavar® Prescribing Information (Fachinformation).

### 1.3.2 Clinical information

Sorafenib has been evaluated in multiple phase-1 and phase-II trials in a variety of advanced tumor types. To date, several 1000 patients have been treated with single-agent and in combination with other commonly used chemotherapeutic agents. In general, Sorafenib can be safely administered to patients on a daily base with most of the dose limiting toxicity events at 800 mg BID. The majority of patients experienced adverse events at some time during the treatment with Sorafenib. Most of these events were not severe and were manageable. Typically, patients experienced skin-related symptoms, either hand-foot skin reaction (HFSR) and/or a rash. Fatigue and diarrhea were also common but usually low to moderate grade. These toxicities resolved once the drug was discontinued. Mild treatment emergent hypertension (rise of 10 mmHg) was reported in about 70% of the patients. However, only the minority of patients will require antihypertensive drugs. There are some pre-clinical models suggesting a potential impact of the inhibition of proapoptotic kinases (ASK1 and MST2) by Sorafenib in drug related cardiotoxicity. Additionally, Sorafenib may interfere with the normal angiogenic response of the heart muscle to volume overload causing dilated cardiomyopathy. However, clinical observations do not support Sorafenib related cardiotoxicity.

Other adverse events reported as drug related include nausea, gastrointestinal symptoms, fatigue, Flu-like symptoms, fever, arthralgia, weight loss, pain, anorexia, diarrhea, dyspnea, abdominal pain, vomiting, pancreatitis, liver function test abnormalities including ALT, AST, GGT, AP and LDH increases, bilirubin increase, dermatitis, erythema, flushing, rash and pruritus, dry skin, alopecia, stomatitis, flatulence, constipation, nail changes, thrombocytopenia, headache, sensory neuropathy, myalgia, amylase elevation, lipase elevation and hypertension.

Currently data from 19 phase-I/II open-label, uncontrolled clinical trials are available for Sorafenib combinations with other anticancer agents. A phase-I study (study code 10916) showed that Sorafenib is suitable for combined administration with doxorubicin in patients with advanced, refractory solid tumors. The most common drug related adverse events were: diarrhea (53%), fatigue (44%), anorexia (44%), hand-foot syndrome (40%), dyspnea (33%),

nausea (35%), rash (33%). Grade 3 and 4 drug related events included: low ANC (74%), increased partial thromboplastin time (15%), increased ALT levels (13%), lymphopenia (13%), low platelet numbers (11%), increased lipase levels (5%). Doxorubicin was given 3-weekly in a dose of 60 mg/sqm for a maximum of 6 consecutive cycles for anthracycline naive patients. Sorafenib was given from 100 mg BID to 400 mg BID. Thereby, dose limiting toxicities (DLT) were reported including HFSR and diarrhea. Less frequently observed DLTs were fatigue, hyperuricemia and asthenia. Most of the trials did not reach a maximum tolerated dose. Thus, Sorafenib is well tolerated even in combination treatment approaches.

Myelosuppression was mainly observed after combination therapy with cytotoxic agents and manifested with leukopenia, neutropenia, febrile neutropenia and thrombocytopenia.

statistically significant improvement versus Placebo: 5.5 months and 2.8 months, respectively (HR 0.44, 95% CI 0.35-0.55,  $p < 0.000001$ ). Consequently, cross-over was allowed for patients on Placebo from May 2005 on. A first interim analysis for survival in May 2005 showed a significant reduction in risk of death for Sorafenib compared to Placebo. (HR 0.72, 95% CI 0.54-0.94,  $p = 0.02$ ). Response rates were also favorable for Sorafenib with an overall response rate (ORR) of 10% (PR) vs. 2% in the Placebo arm ( $p < 0.001$ ). A second analysis on survival showed a median OS of 19.3 months vs. 15.9 months (HR 0.77, 95% CI 0.63-0.95,  $p = 0.015$ ). These data led to registration of Sorafenib in the USA and Europe for the treatment of advanced renal cell cancer.

In the hepatocellular cancer (HCC) study, 602 previously untreated patients were randomized into an international multicenter Placebo-controlled phase-III trial and received either Sorafenib 400 mg BID or Placebo. Primary endpoint was OS. A planned interim analysis showed a significant survival benefit of Sorafenib (10.7 months vs. 7.9 months; HR 0.69, 95% CI 0.55-0.87,  $p = 0.0006$ ). These data led to registration of Sorafenib in the USA and Europe for the treatment of advanced hepatocellular cancer in 2007.

For further information about clinical data of Sorafenib, please refer to the current Nexavar® Prescribing Information (Fachinformation).

## **2 STUDY AIM AND DESIGN**

### **2.1 Rationale for this study**

Sorafenib is a potent inhibitor of wild type and mutant Raf kinases. There are abundant preclinical data suggesting that the Ras/Raf pathway may be activated and associated to pathogenesis of AML and MDS rendering Raf kinase a potentially suitable target in the treatment of these conditions. In addition, Sorafenib inhibits the MAP kinase pathway by targeting p38 kinase. Furthermore, 30% of AML patients have FLT3 activating mutations. Sorafenib is also a potent inhibitor of a mutant form of the Flt3 kinase (Flt3-ITD) and thus may be especially effective in this subgroup of AML patients. Sorafenib inhibits also c-Kit, which is present in AML blasts in 70%. Furthermore, it may be hypothesized that the angiogenesis receptor tyrosine kinases VEGFR-2 and PDGFR may play a role in the pathogenesis of AML either in regard to vascularisation of the bone marrow stroma or as growth factors on leukemic blasts. In a phase-I trial with Sorafenib as a single agent at escalating doses the drug has shown efficacy in 56% out of 16 AML patients. The response was mainly restricted to blast response in FLT3-ITD positive patients. Subsequently, it was reported that Sorafenib has inhibitory efficacy on a range of antiapoptotic molecules. This activity can lead to an enhanced antileukemic efficacy when combined with cytotoxic drugs in AML cells. Therefore, Sorafenib as a single cytostatic agent is unlikely to be a curative treatment. The present study investigates the effects of Sorafenib, when applied between and after cycles of standard chemotherapy for AML.

### **2.2 Benefit / risk ratio**

Patients eligible for this trial have a risk of treatment failure with standard chemotherapy of 50-60% at two years. Treatment failure is an acutely life-threatening event for these patients. Included in these numbers are disease-related events (refractory disease, relapse) and treatment-related mortality that has to be expected to reach up to 10% in this patient group. The risk of this trial is that addition of Sorafenib to the standard treatment increases treatment-related toxicity. However, as pointed out above, phase-I/II trials indicate that Sorafenib can be administered safely in combination with cytotoxic drugs. Whether this is also true for the trial population is one of the objectives of this study.

The possible benefit of the trial is to decrease the rate of treatment failure in the trial population. For a single patient, this could result in increased life-span, ideally without evidence of leukemia. Given the high rate of treatment failure and the high toxicity of the currently available standard therapy, the medical need for novel, rational therapeutic approaches for this patient population is overwhelming. As pointed out above, the molecular rationale for the therapeutic

administration of Sorafenib in AML is well founded. Thus, the Benefit/Risk ratio for a patient to participate in this trial seems very favorable.

## **2.3 Study objectives**

### **2.3.1 Primary**

- to compare the median Event Free Survival (EFS) of AML patients in the age of  $\geq 18$  and  $\leq 60$  years between the Sorafenib and the control group (for event definition see chapter 7.2.1)

### **2.3.2 Secondary**

- to compare the median EFS of AML patients with Flt3-ITD mutations between the Sorafenib and the control group
- to compare the median EFS of the patients in each of the six strata:
  1. HR cytogenetics: yes
  2. LR cytogenetics: yes
  3. HR and LR cytogenetics: no and NPM1-Mut: yes, Flt3 Mut: yes
  4. HR and LR cytog.: no and NPM1-Mut.: yes, Flt3 Mut.: no
  5. HR and LR cytog.: no and NPM1-Mut.: no, Flt3 Mut.: yes
  6. HR and LR cytog.: no and NPM1-Mut.: no, Flt3-Mut.: no
- to compare the median Overall Survival (OS) of AML patients with Flt3-ITD mutations between the Sorafenib and the control group
- to compare the median Overall Survival (OS) of all AML patients between the Sorafenib and the control group
- to compare the CR rate of the Sorafenib with the control group
- to compare the rate of molecular remissions of the Sorafenib with the control group
- to compare the toxicity of the Sorafenib and the control treatment
- to compare the evidence of minimal residual disease of all AML patients between the Sorafenib and the control group after induction therapy and in the course of the first remission
- to compare early treatment efficacy (day 16 bone marrow assessment) between the Sorafenib and the control group
- to compare the development of biomarkers indicating the course of disease, including genetic, epigenetic, transcriptional and protein markers in leukemic blasts, bone marrow, peripheral blood cells, serum and plasma

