## 7 STUDY OUTCOME AND STATISTICAL ANALYSIS

### 7.1 Power and Sample Size Calculation, Interim Analysis

Power calculations are based on the following assumptions:

Control group:	median event free survival (EFS) 9 months
Sorafenib group:	median event free survival (EFS) 13.5 months (improvement of 50%)
Error of first kind:	$\alpha = 0.05$ (two sided)
Power:	80%
Accrual time:	24 months
Follow up:	18 months
Randomization:	1/1 allocation

To detect an improvement of median EFS from 9 months to at least 13.5 months, we need 125 evaluable patients per group i.e. a total of 250 patients to yield the necessary number of approximately 191 events.

Although all efforts will be taken to avoid patient loss to follow up, there might be a rate of loss due to various possible reasons. Censoring by transplantation in first remission will lead to an additional loss. The rate of allogeneic transplantation is assumed with about 10% of the patients. Patients receiving allogeneic stem cell transplantation will be censored for analysis at the time point of transplant. In order to account for this, exponential hazard of 0.0074 is incorporated in the sample size calculation.

Within 24 months the participating centers are able to recruit up to 300 patients fulfilling the inclusion and exclusion criteria. Taking into account a drop out rate of about 10 % the study-centers will recruit the necessary number of patients (n=276) within 24 months.

All calculations are done using SAS-Software (PROC POWER) licensed to the University of Münster.

One interim analysis and the final analysis are planned for the intent-to-treat EFS endpoint such that the overall type I error is controlled at a two-sided 0.05 level. Interim analysis will be done according to the O'Brien/Flemming approach. When 50% of the expected intent-to-treat EFS events (191 events  $\times$  0.5 = 95) are attained the first interim analysis on the intent-to-treat EFS endpoint will be conducted.

The (unblinded) interim analysis will be performed by the Studienzentrale SAL in cooperation with Institut für Medizinische Informatik und Biometrie, Münster.

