## **7.2 Statistical Analysis Plan**

We assume an accrual time of 24 months and a follow-up time of 18 months.

The statistical analysis will be performed according to the intention to treat principle (ITT analysis). This means that every patient included into the study and randomized to one treatment arm will be evaluated in that arm, even if he does not receive study-medication, or if any other violations of the study protocol occur.

- The primary endpoint (median EFS) will be compared between both treatment arms using two-sided stratified log-rank test as described in detail. This part of the analysis is considered as confirmatory.
- Analyses of secondary endpoints will include morphologic CR-rate, overall survival, leukemia free interval and leukemia free survival.
- In an exploratory approach EFS and OS will be analyzed using stratified Cox-regression. Treatment arm and cytogenetic findings will be included as independent variables. The results of these analyses will be considered as exploratory. No  $\alpha$ -adjustment will be performed.
- In addition to the ITT-analysis a per protocol analysis (PP-analysis) will be performed. This analysis will include only those patients who could be treated with full adherence to the protocol. Besides this, the PP-analysis will parallel the ITT-analysis.

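### Subgroup efficacy is planned only as separate EFS comparisons in Flt3-ITD and in each of six strata, which cannot show whether the effect differs and would usually make a uniform effect look selective

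*Protocol*

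**What the plan says.** Protocol 2.1 gives the molecular rationale and states that Sorafenib "may be especially effective in this subgroup of AML patients", meaning patients with Flt3-ITD. Section 2.3.2 turns this into arm comparisons inside subgroups: "to compare the median EFS of AML patients with Flt3-ITD mutations between the Sorafenib and the control group", the same for overall survival, and "to compare the median EFS of the patients in each of the six strata".

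Section 7.2 names the primary EFS comparison, a two-sided stratified log-rank test, as the confirmatory part. On secondary endpoints it says "Analyses of secondary endpoints will include morphologic CR-rate, overall survival, leukemia free interval and leukemia free survival"; the stratum and Flt3-ITD comparisons are not in that list. It then plans a stratified Cox regression of EFS and OS with treatment arm and cytogenetic findings as covariates, of which it says "The results of these analyses will be considered as exploratory". That model has no Flt3 covariate and no treatment interaction.

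Neither section gives a test, a significance threshold or a rule of interpretation for the subgroup comparisons.

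**The concern.** Whether a drug is especially effective in one group is a question about the difference between its effect there and its effect elsewhere. A Sorafenib-versus-placebo comparison inside Flt3-ITD patients estimates the effect in that group. It says nothing about the difference unless it is set against the other patients with a measure of uncertainty. The same holds for six separate stratum comparisons.

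Without an estimate of the difference, readers tend to sort strata into those that reached significance and those that did not. With about 250 evaluable patients over six strata, that sorting mostly reflects chance and stratum size. At stake is the interpretation of the biological question behind the trial: a uniform benefit could be reported as confined to some strata, or a chance result in one stratum as a genetic signal.

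**Working it through.** **Inputs from the protocol (7.1 and 2.3.2).** Control "median event free survival (EFS) 9 months"; Sorafenib median 13.5 months; 1:1 allocation; two-sided 0.05; 80% power; about 191 events; 250 evaluable patients; six disjoint strata.

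**Assumptions, not stated in the protocol.** Each subgroup is tested by log-rank at a nominal two-sided 0.05. Events are split equally over strata unless noted. The Flt3-ITD share of events is taken as 20% to 30%.

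**1. The plan's own figure.** With exponential survival the hazard ratio is 9/13.5 = 0.667, so |ln HR| = ln 1.5 = 0.4055. Schoenfeld's formula gives 4 × (1.960 + 0.842)² / 0.4055² = 191 events. The stated number reproduces.

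**2. No effect anywhere.** The strata are disjoint, so the six tests are independent.
- At least one nominally significant stratum, either direction: 1 − 0.95⁶ = 26.5%.
- At least one in favour of Sorafenib: 1 − 0.975⁶ = 14.1%.
- Adding the Flt3-ITD comparison, which overlaps the strata, gives 28–29% and about 15% by simulation.

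These rates barely depend on stratum sizes.

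**3. The same benefit (HR 0.667) in every stratum.**
- Events per stratum: 191/6 = 31.8.
- Expected test statistic: 0.4055 × √31.8 / 2 = 1.144.
- Power per stratum: Φ(1.144 − 1.960) = 0.207, or 0.208 counting both tails. It is 9% at a 5% share of events and 34% at a 30% share.
- Some but not all six significant: 1 − 0.792⁶ − 0.208⁶ = 1 − 0.247 − 0.0001 = 75%. An unequal split (event shares from 8% to 32%) gave 76% by simulation.
- All six significant: under 0.01%.
- At least one stratum estimate pointing against Sorafenib: 1 − Φ(1.144)⁶ = 1 − 0.874⁶ = 56%; 60% under the unequal split.

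**4. Flt3-ITD against the rest, same uniform benefit.**

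| Flt3-ITD share of events | Power inside | Power outside | Exactly one group significant |
|---|---|---|---|
| 20% | 0.24 | 0.71 | 0.24 × 0.29 + 0.76 × 0.71 = 61% |
| 30% | 0.34 | 0.65 | 0.34 × 0.35 + 0.66 × 0.65 = 55% |

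Even if Sorafenib works in Flt3-ITD patients exactly as assumed for the whole trial, the comparison inside that group would miss significance in about two to three trials out of four.

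**The case against.** The strongest reply has four parts.

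First, testing order, alpha allocation and model terms for secondary analyses are commonly left to a statistical analysis plan, and none is shown here. This stands: the lack of a hierarchy or an alpha split is not an error in this protocol.

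Second, the status of these comparisons is largely settled. Section 7.2 keeps the confirmatory label for the primary test, and 7.1 states for the ITT EFS endpoint that the "overall type I error is controlled at a two-sided 0.05 level". This also stands. A reader might infer that the subgroup comparisons inflate the trial's type I error or allow efficacy to be claimed in one stratum after a failed primary. The protocol provides for neither.

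Third, the stated objective is the effect within Flt3-ITD patients, for which a within-group comparison is the right estimator, and the strata are prespecified randomization strata rather than post hoc cuts. That is correct for the objective as worded. But the reason for singling out these patients in 2.1 is a differential effect, and no analysis in the document addresses it.

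Fourth, the protocol names no p-value threshold for the strata, so the error rates describe an assumed reading. This is fair, and the figures are conditional on it. It is nevertheless the usual way such comparisons are read, and the text does nothing to prevent it.

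**Conclusion.** The concern holds in a limited form. The protocol addresses subgroup efficacy only by separate arm comparisons, and its one regression model lacks the terms that would estimate a difference in effect by stratum or by Flt3-ITD status.

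The stronger argument is the uniform-benefit case: at the design effect with equal strata, power is about 21% per stratum and about three trials in four would show a mixture of significant and non-significant strata. The null case gives 26.5% for a false stratum difference in either direction. A reader might take that as one null trial in four producing a false win for Sorafenib, but the figure for a win is about 14%, or one in seven.

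These results rest on the nominal 0.05 reading. The per-stratum power also rests on the assumed event shares. Stratum sizes are not given, and events in the high-risk stratum may be fewer because section 4.3.3.3 directs those patients to transplantation with censoring. The 75% figure changes little under the unequal split examined. The primary analysis and its error rate are not affected.

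**What to change.** In 7.2, add two tests to the planned exploratory Cox model for EFS:
- treatment by stratum across the six strata (5 df);
- treatment by Flt3-ITD (1 df), with a Flt3-ITD main effect. Define it by ITD status itself. The strata use Flt3 mutation status only outside high- and low-risk cytogenetics, and section 5.4 lists both ITD and point mutations for stratification, so no union of strata equals the Flt3-ITD group.

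Keep the comparisons in 2.3.2, but state that they are reported as hazard ratios with 95% confidence intervals and without significance claims within strata. Label strata by their definition rather than their number, because 2.3.2 and Table 1 number strata 3 and 4 in opposite order.

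The cost is a few sentences and model terms; no extra patients, data or visits. The sponsor gives up the option of pointing to a single stratum's unadjusted p-value. The real limit is power. With Flt3-ITD at 30% of events, the standard error of the difference in log hazard ratios is √(4/57.3 + 4/133.7) = 0.316, so 80% power needs a ratio of hazard ratios of exp(2.80 × 0.316) = 2.4. At 20% it is √(4/38.2 + 4/152.8) = 0.362, and the ratio is 2.8. A non-significant interaction therefore would not show that the effect is the same everywhere, and the text should say so.
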